PTK (IE global)	Dependent	Quantitative	Continuos, Ratio	IE (***)formula)	FOCOS
Executive functions "component" 1	Dependent	Quantitative	Discrete, interval Continuos, Ratio	Number of Hits/Errors Time (sec, min)	Tower of Hanoi
Problem solving "component" 2	Dependent	Quantitative	Discrete, interval	Number of Hits/Errors	Tower of Hanoi

Cognitive flexibility			Continuous, Ratio	Time (sec, min)	
"Component" 3 Impulse control	Dependent	Quantitative	Discrete, interval	Number of Hits/Errors	Stroop test
"component" 4 Visuospatial working memory	Dependent	Quantitative	Discrete, interval	Number of Hits/Errors	Corsi Cubes
"Component" 5 Executive Attention	Dependent	Quantitative	Continuous, Ratio	Time (sec, min)	Trail Making Test (TMT)
"component 6" Sustained attention	Dependent	Quantitative	Discrete, interval	Number of Hits/Errors	Crossing out boxes
			Continuous, Ratio	Time (sec, min)	
Age	Confounding	Quantitative	Continuous, Ratio	Years and months	Survey
Sports age	Confounding	Quantitative	Continuous	Years	Survey
Playing position	Confounding	Qualitative	Nominal	Lateral, Central, Midfielder, Winger, Forward	Survey
Socioeconomic	Confounding	Qualitative	Ordinal	Scale from 1 to 6	Bill of public services of the house
Educational level	Confounding	Qualitative	Ordinal	School grade	Survey
Mass	Confounding	Quantitative	Continuous, Ratio	(kg)	Scale
Height	Independent	Quantitative	Continuous, Ratio	(cm)	Stadiometer
IMC	Confounding	Quantitative	Continuous, Ratio	(kg/m ²)	Equation
Mental fatigue	Confounding	Qualitative	Ordinal	Scale from 0 to 100	Question

Notes:

*Offensive effectiveness indices (IE) = Sum of the IE of the offensive tactical behaviors/Number of categories in which the soccer player developed offensive tactical behaviors.

** Defensive IE = Sum of the IE of the defensive tactical behaviors/N° of categories in which the Soccer players developed defensive tactical behaviors

*** Global IE = Offensive IE + Defensive IE/2

Masking

People who carry out the assessments are masked (they do not know which group the athletes were assigned to). In order to carry out an adequate strategy to control information biases, the professionals who carry out the evaluations are masked (blinding). Consequently, the evaluators of the primary, secondary, and exploratory outcomes were masked as follows:

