PTK (offensive, defensive, and global IE) (expert soccer coach, licensed A soccer coach from the Colombian Federation, video analyst with excellent knowledge and management of videoanalysis's software such as Nacsport and he is an expert of observation categories and trained in the FOCOS (Football Competence Observation System) evaluation instrument, as well as in the management of the LINCE PLUS software).

Executive functions (problem solving, cognitive flexibility, impulse control, visuospatial working memory, executive attention, and sustained attention). These evaluations are developed by the neuropsychologist.

Professional who carry out the anthropometric evaluations is masked, she is researcher with training in sports training and use of scales and height rods.

Person who applies the survey to the soccer players to inquire about the sociodemographic characteristics of the population is masked too.

In the same way, the professional who asking to the research participant are masked too, which inquiries about the level of mental fatigue that they perceive just before the evaluations of executive functions and the FOCOS test.

The evaluations are carried out by expert professionals, with training and experience in each of the areas as described in the previous section, which guarantees their reliability. The evaluators of each of the areas mentioned above only carry out the tests (pretest and posttest) and intermediate tests 1 and 2 for the offensive, defensive, and global IE. These evaluators will report the results to the principal researcher, who in turn will file them on a personal computer with a password so that no one else has access to the information and will make backup copies in the cloud. In this way, this level of the investigation will be masked. Subsequently, the principal researcher will send the data to the statistician to proceed with data processing and information analysis.

In the same way, the statistician who will analyze the data will be masked, in this sense, the statistician will not know the identity of the participants he is analyzing, he will process data from coded subjects. The statistician will also not know to which comparison

group the data of the participants he will analyze belongs. In this way, 2 levels of the study will be masked (evaluators and data analysis).

Ethical aspects

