To obtain the data, the games must be filmed with a camera and later, carry out the respective analyzes and evaluations. In the present investigation, a DJI Fly drone is used, which is positioned 20m high just behind one of the goals, this location guarantees complete visibility of the ATTs executed by the participants and full coverage of the pitch. Once all the corresponding games have been filmed, the videos are downloaded, which are

sent to the video analyst who will carry out the respective analysis and data report in the database created for this purpose. For the analysis, the video analyst will use the LINCE PLUS video analysis software (Soto et al., 2019), which is available and freely accessible.

The FOCOS units of measure are:

Volume, which corresponds to the number of times the soccer player develops tactical behaviors in each category.

The IE is determined through the following formula:

$$IE = \text{Volume of successful tactical behaviors} / \text{Number of tactical behaviors developed in each category of analysis}$$

$$\text{Offensive IE} = \text{Sum of the IE of offensive tactical behaviors} / \text{Number of categories in which the soccer player developed offensive tactical behaviors}$$

$$\text{Defensive IE} = \text{Sum of the IE of defensive tactical behaviors} / \text{Number of categories in which the soccer player developed defensive tactical behaviors}$$

$$\text{Global IE} = \text{Offensive IE} + \text{Defensive IE} / 2$$

The global IE represents the PTK of each soccer player.

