The construct validity of the instrument was calculated from its perspective of discriminant validity, which allows measuring the degree of the instrument to differentiate between groups of soccer players that are expected to be different. To do this, they compared two independent samples (semi-professional soccer players and amateur soccer players). The data were analyzed using the student t test for independent samples and the results showed significant differences ($p \leq 0.05$). In addition, they calculated the effect size (ES) using Cohen's d to assess the magnitude of the difference between groups of soccer players (Cohen, 1988). According to the Hopkins et al. (2009) established the ES as (very large: $d = >2$; large: $d = 1.2$ to 2.0 ; moderate: $d = 0.6$ to 1.2 ; small: $d = 0.2$ to 0.6 and trivial: $d = 0$ to 0.2). The results showed values between 1.08 and 2.32 in favor of the group of semi-professional soccer players, except for 1 variable that showed differences in favor of the group of amateur soccer players.

The calculation of the intra-observer stability index was carried out through test-retest reliability, for which Cohen's Kappa (k) was applied to the data extracted with a difference of five weeks in the evaluation of both records. The results showed an agreement index of $K = 0.747$ considered as a good agreement (Altman, 1991).

For the present research, the calculation of the intra-observer stability index will be carried out through the test-retest reliability with a difference of five weeks between both observations. For this, the videos and ATT of two soccer players will be observed and the results will be compared through the Kappa index (k). When the evaluator (video analyst) obtains an agreement considered good (0.61 - 0.80) or very good (0.81 – 1.00) (Altman, 1991, slightly adapted from Landish and Koch, 1977), the videos will be evaluated and record the respective data.

The inter-observer reliability of FOCOS was calculated using the inter-observer agreement coefficient for more than two observers ($n = 3$). In this case, the Kappa Fleiss was applied. The results showed a concordance coefficient of $K = 0.766$ considered as a good agreement.

The PTK evaluations will take place on the synthetic grass field of the UdeA.

Executive functions

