research protocol, that is, pretest (week 1), intermediate test 1 (week 6), test intermediate 2 (week 11) and posttest (week 16). Likewise, the groups formed randomly and the confrontation between them determined by chance at all test will be respected. If for any reason a participant cannot take the test due to any circumstance (absence at the session, physical discomfort, momentary bruises, injury or unexpected situations), his replacement will be arranged with IUEFD student with experience as soccer players and who previously know the protocol to complete the gap, or with soccer players who are on trial at the club and who are not part of the comparison groups. The tests will be carried out on Wednesday from 6 to 8 in the morning in the respective weeks (1, 6, 11 and 16).

Once the tests have been completed and duly filmed, the respective videos will be passed on to the evaluator (video analyst) who will download the videos, analyze the different actions and behaviors developed by each of the participants through the LINCE PLUS video analysis software and record the data in Excel files in the database created for this purpose. This database will be created in such a way that a code is generated for the participants and no one can identify who the information registered and consigned there corresponds to (except the main researcher) who will save it on their personal computer, on a hard drive to keep copy and in the cloud. These files will be kept with a password, which only the principal researcher will know.

The information and data resulting from the respective analyzes carried out by the evaluator will be sent to the statistician who will proceed to carry out the respective analysis and application of tests in accordance with the data treatment that appears in the data analysis section.

Prior to carrying out the FOCOS test that evaluates the primary and secondary outcomes and, prior to the execution of the tests that evaluate executive functions (exploratory outcome), the following question will be asked to the participants: from 0 to 100, ¿How mentally fatigued are you? Being 0 (not at all fatigued) and 100 (maximum fatigue).

The evaluations of week 1 were carried out on two different days and in the following order: the first day the survey was carried out, mass, height, mental fatigue and finally, the tests were applied to assess the executive functions, for which participants were

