summoned by groups of 4 every hour. Total application time from full battery was approximately 60 minutes. On the second day, the FOCOS field test was carried out and all the participants were summoned at 6 in the morning. In the intermediate tests 1 (week 6) and 2 (week 11) only the evaluations will be carried out through FOCOS. Finally, the post-test evaluations (week 16) will be carried out in the same way as in the pre-test, that is, they will be carried out on two different days and in the following order: the first day the tests will be applied to assess the executive functions and mental fatigue, on the second day, the field test (FOCOS) will be carried out, for which all the participants will be summoned at 6 in the morning.

Bias Control

To control biases in the different stages of the study (planning, execution, and data analysis), different strategies and actions were established to obtain reliable results. Bias control was carried out as follows:

Control of Allocation Biases (Randomization Biases)

To avoid these biases, the participants were randomized to two comparison groups (GE and CG) as previously described in the randomization process.

Control of Information Biases (Systematic Biases)

To avoid these biases, reliable and valid protocols and tests are used, in addition, the evaluation protocols were standardized (pretest, intermediate test 1, intermediate test 2 and posttest), which will be carried out under similar conditions, with the same equipment and by the same evaluators). In the same way, the equipment and instruments were calibrated in accordance with quality norms and standards. It is important to mention that the personnel that carry out the evaluations and interventions are experts in their respective areas and that those necessary for the development of a protocol or intervention were trained. In addition, the evaluator of the actions related to the PTK and the IE (offensive, defensive, and global) must demonstrate and achieve a good stability, which will be obtained and calculated through test-retest, once the evaluator achieves a score for above 0.6 the PTK evaluation process will continue in the research.

Confounding Bias Control

To avoid these biases, confounding variables (age, sporting age, playing position, socioeconomic status, educational level, mass, BMI, and mental fatigue) will be controlled.

The study has masking (blinding) at two levels (assessments and data analysis).

Analysis of data

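### The single FOCOS analyst is masked to group but not to test wave, and the scoring order is not fixed, so rater drift could bias the time and within-arm results for the effectiveness index (IE)

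*Combined protocol and SAP*

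**What the plan says.** **Masking.** The Masking section defines assessor masking by allocation alone: "People who carry out the assessments are masked (they do not know which group the athletes were assigned to". It closes by counting what is concealed: "In this way, 2 levels of the study will be masked (evaluators and data analysis". Test wave is not mentioned.

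**Who scores.** The FOCOS video analyst is described in the singular throughout. Under Control of Information Biases, all tests are to be run "with the same equipment and by the same evaluators". He judges each action as successful or wrong, with a further code for doubtful cases, and IE is built from those success codes (Information Collection Instruments, PTK).

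**When he scores.** There are two descriptions. Data Collection Procedures: "Once the tests have been completed and duly filmed, the respective videos will be passed on to the evaluator (video analyst". The PTK instrument section: "Once all the corresponding games have been filmed, the videos are downloaded, which are" sent to the analyst. Neither says whether it refers to one wave or to all four.

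**What is hidden in the files.** In the database, "a code is generated for the participants". No removal of dates or wave labels and no random scoring order is described. The analyst downloads the videos himself.

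**Stability check.** Two readings are made five weeks apart: "the videos and ATT of two soccer players will be observed and the results will be compared through the Kappa index (k". Scoring starts once kappa is in the good range (0.61 to 0.80) or better. Pilot Testing Procedures and Bias Control repeat this as a condition of entry. No later check is stated.

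**Analysis.** Analysis of data specifies repeated-measures ANOVA or Friedman over the four tests for offensive, defensive and global IE, plus a MANOVA whose factors are not given. No group-by-time contrast is named for IE.

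**The concern.** The codes are judgements made by one person on footage that spans 15 weeks. If he knows which test he is watching, or scores the tests in date order, two things can move the scores without any change in play. His standard may drift as he gains practice, and he may expect players to do better later. Either is then indistinguishable from real change over time. Masking to group does not remove this, because a later wave is later for both arms.

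The results at stake are the time effect and the change within each arm. The Objectives section asks about the programme's effect on procedural tactical knowledge over 12 weeks, so a rise from week 1 to week 16 is likely to be read as a result. The exposure is greatest if normality fails. Friedman has no group factor, so it would report drift shared by both arms as improvement.

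**Working it through.** **Inputs from the documents**
- 24 players, 12 per arm, 1:1 (Sample Size Calculation, Randomization Process). The stated difference of 1.13 and SD of 0.81, with a two-sided 0.05 t-test (sidedness assumed for the sample size), give 12 per arm and power 0.904. The figure of 24 reproduces and is not in dispute.
- Four waves: weeks 1, 6, 11 and 16.
- Significance level 0.05 (Analysis of data).

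**Assumed inputs (the documents give none)**
- Drift D: total shift in scoring from week 1 to week 16, in units of the SD of IE at one wave, linear and equal in both arms. Range 0.2 to 0.5.
- Within-player correlation ρ between waves: 0.5 and 0.7.
- No true change in either arm.

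**Formula for the time effect.** The drift at the four waves is D × (0, 1/3, 2/3, 1). The squared deviations from its mean sum to D² × (1/4 + 1/36 + 1/36 + 1/4) = (5/9)D². With residual variance 1 − ρ, the noncentrality is

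λ = 24 × (5/9) × D² / (1 − ρ),

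on 3 and 2 × 11 × 3 = 66 degrees of freedom, where the 5% critical value is F = 2.74. For D = 0.5 and ρ = 0.5, λ = 24 × 0.5556 × 0.25 / 0.5 = 6.67, and the chance of exceeding 2.74 is 0.54.

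| D | ρ | λ | false positive, formula | false positive, simulation |
|---|---|---|---|---|
| 0.2 | 0.5 | 1.07 | 11.6% | 11.5% |
| 0.2 | 0.7 | 1.78 | 16.7% | 16.6% |
| 0.3 | 0.5 | 2.40 | 21.4% | 21.8% |
| 0.3 | 0.7 | 4.00 | 33.9% | 34.7% |
| 0.5 | 0.5 | 6.67 | 53.9% | 54.2% |
| 0.5 | 0.7 | 11.11 | 78.2% | 78.0% |

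The simulation used 4,000 trials per setting. With no drift it gave 5.2% and 5.6%.

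**Other tests in the same simulation**
- Friedman within one arm of 12, D = 0.5: 21% to 33%.
- Paired week 1 to week 16 test within one arm, D = 0.5: 36% to 53%.
- Group-by-time, D from 0.2 to 0.8: 4.6% to 5.9%.
- Between-arm test of change, same range: 5.0% to 5.6%.

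The last two stay at the nominal level because a shift common to both arms cancels in the difference between arms.

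**Reach of the stability check.** It compares two readings five weeks apart and is passed before scoring starts. The waves are also five weeks apart (6 − 1, 11 − 6, 16 − 11), so it speaks to stability over one such gap. It does not observe the analyst over the 15 weeks of the study. It uses two of 24 players and is not repeated.

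**The case against.** The strongest reply is that the trial compares two randomised arms, and the calculation above shows that shared drift leaves that comparison at its nominal error rate. This stands, with group masking as the condition. A reader might go further and infer that the arm contrast is biased too, because drift could differ by playing style or score level. Nothing in the documents supports that.

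A second reply is that wave-by-wave scoring is not stated. This also stands. A reader might infer that videos go to the analyst as each test is filmed, but the two release sentences fit a single batch after week 16 equally well. The gap remains under either reading, because a batch scored in date order with dates visible has the same weakness. The absence of wave masking is likewise an omission in the plan, not a stated decision to unmask.

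A third reply is that change over time is not a randomised comparison. Both arms train five times a week, play weekly matches and repeat the test, so a time effect could not be credited to the programme even with perfect scoring. That is right and limits the weight of the point. It does not remove it, since the analysis plan tests IE over time and names no group-by-time contrast. Naming that contrast as the test of effect would be a separate improvement. It would reduce the consequence but would leave the time and within-arm results unprotected.

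Finally, the entry kappa is some control, and its interval is well chosen. It is thin, and it says nothing about later waves.

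**Conclusion.** The point holds as a gap in the plan that should be closed. One analyst makes judgement codes at all four tests, masking is defined by group only, scoring time and order are open, and no stability check follows entry. Drift or expectation would bias the time effect and within-arm change in IE. The randomised group-by-time contrast is largely protected if group masking holds, so this does not threaten the between-arm conclusion.

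The size is conditional. At an assumed drift of 0.2 to 0.5 SD, with correlation 0.5 to 0.7 and drift linear and equal in both arms, the time effect is falsely significant in about 12% to 78% of trials. The documents give neither a drift nor a correlation, so these figures show sensitivity and do not estimate what will happen. The plan as written would not reveal the drift if it occurred.

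**What to change.** In Data Collection Procedures, state that the videos are held until week 16 has been filmed. The principal researcher, who already delivers the pilot videos to the analyst under Pilot Testing Procedures, removes dates and wave labels and supplies the games of all four waves in one random order. The same analyst scores each game once. The analyst should no longer download the original files himself. Extend the Masking section to read 'masked to group and to test wave'.

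No second reader is needed. The footage is small: if the 24 players form six teams of four and each team meets one opponent (an assumption), it is 3 match-ups × 2 games × 4 minutes × 4 waves = 96 minutes, although coding takes longer than running time.

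The costs are a relabelling step, scoring concentrated at the end, and no IE results before week 16; the plan describes no interim decision that needs them. Weather or light may sometimes reveal the wave, but random order still prevents drift from tracking time. The pretest is described as already carried out, so any pretest videos already scored must be rescored in the batch.

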
Players with musculoskeletal disorders at the time of sample selection.

Players recovering from injury.

Sample Size Calculation

A systematic probabilistic sampling of permuted blocks was carried out, for which the Epidat software, V. 4.2, was used. Taking into account the study by Sierra-Ríos et al., (2020) in which they report a mean difference of 1.13 and a standard deviation of 0.81, 5 scenarios were established to calculate the sample size (with powers of 80, 85, 90, 95 and 99%). Based on these five scenarios, the samples found are:

Scenario 1 (80% power): (20 soccer players. GE = 10 and GC = 10).

Scenario 2 (85% power): (22 soccer players. GE = 11 and GC = 11).

Scenario 3 (90% power): (24 soccer players. GE = 12 and GC = 12).

Scenario 4 (95% power): (30 soccer players. GE = 15 and GC = 15).

Scenario 5 (99% power): (40 soccer players. GE = 20 and GC = 20).

Based on these results of the calculation of different sample sizes, it decided to work with scenario 3 described above.

Randomization Process

To carry out the randomization sequence generation method, a sequence of permuted blocks of 4, 6 was generated. The relationship between groups is 1:1, for which the random assignment software (simulation) was used <https://www.sealedenvelope.com/simple-randomiser/v1/lists>.

The allocation was concealed by means of sealed and opaque envelopes, for which the 24 envelopes were available for each one of the participants. The envelopes were numbered from 1 to 24, the name of each research participant was added to them along with a sheet of carbon paper and the name of each research participant was marked for each intervention experimental group (GE) and control group (GC). This process of randomization sequence generation, allocation concealment, and allocation was performed by someone other than the research staff.

Variables

The study's variables, their operationalization, function, nature, measurement scales, units of measurement and instruments used are described in Table 1.

Table 1. Variables and their operationalization

Variable	Function	Nature	Scale	Unit of measurement/values	Instrument
PTK (Offensive IE)	Dependent	Quantitative	Discrete, interval Continuos, Ratio	Volumen (N° of times the action is performed) IE (*formula)	FOCOS
PTK (IE Defensive)	Dependent	Quantitative	Discrete, interval Continuos, Ratio	Volumen N° of times the action is performed) IE (**formula)	FOCOS

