To establish the distribution of the data of the quantitative variables, the Shapiro-Wilk test will be applied. The variables that present a normal distribution will be summarized with means and standard deviation. Variables that present a non-normal distribution will be summarized with medians and interquartile ranges. Likewise, the qualitative variables will be presented in absolute and relative frequency tables.

To establish the behavior of the offensive, defensive, and global IE, a repeated measures design will be carried out that includes 4 evaluations over time (pretest, intermediate test 1, intermediate test 2 and posttest). For this, an ANOVA of repeated measures or the Friedman test will be used according to the normality of the variables, in addition, the assumption of homogeneity of the variances will be evaluated based on the Levene statistic. Since different dependent variables will be evaluated, a multivariate analysis of variance (MANOVA) will also be performed.

For the variables related to executive functions, an intragroup analysis of each of the groups (GE and GC) will be carried out, comparing the pretest and posttest values to establish possible differences, for which the dependent student t test or the Wilcoxon test of according to its distribution. In addition, an intergroup analysis will be carried out to compare the possible differences between the groups (GE and GC), for which the student t test for independent samples or the Mann Whitney U test will be applied according to the distribution of the variables. Similarly, confidence intervals (CI95) and two-tailed effect sizes will be reported, with alpha (α) set to 0.05 and statistical power 0.8 (1- β). The statistical significance value is set at $p \leq 0.05$. An analysis of the information will be carried out using the statistical package SPSS version 27 and the software R free version 4.0. Procedures will be carried out to detect possible inconsistencies in the measurements and to identify outliers and extreme values. Likewise, if necessary, statistical adjustments will be made. Intention-to-treat analysis will be performed.

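### Eight variables are promised control in a 24-player trial, but no planned analysis contains a covariate; the plan should say what is adjusted for, how, and with which measurement

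*Combined protocol and SAP*

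**What the plan says.** Under Bias Control, the Confounding Bias Control section states without condition that "confounding variables (age, sporting age, playing position, socioeconomic status, educational level, mass, BMI, and mental fatigue) will be controlled". It gives no method. Table 1 labels all eight as confounding; playing position has five nominal categories and socioeconomic level runs from 1 to 6.

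Analysis of data names repeated-measures ANOVA or Friedman for the effectiveness indices (IE), then MANOVA, and t, Wilcoxon or Mann-Whitney tests for executive functions. None is given a covariate. The only related wording is "if necessary, statistical adjustments will be made".

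Sample Size Calculation cites a study said to "report a mean difference of 1.13 and a standard deviation of 0.81" and adopts "Scenario 3 (90% power): (24 soccer players. GE = 12 and GC = 12"). It makes no allowance for covariates. Randomization Process describes permuted blocks and says "The relationship between groups is 1:1"; it describes no stratification by any of the eight variables.

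**The concern.** The commitment and the analysis section do not meet. That leaves three possibilities: the promise is not kept, all eight variables enter a model that 24 players can barely support, or a subset is chosen once the data are in hand. The second can cost much of the power the sample size was meant to provide. The third lets the choice of covariates follow the result.

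Timing adds a further gap. Mental fatigue is asked before every FOCOS test and before the executive-function tests. Mass and BMI are taken at the start and at the end. A value recorded after training begins may itself have been changed by training, and adjusting for it can remove or distort part of the effect. The plan does not say which value would be used.

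**Working it through.** **1. The plan's own figure.** Inputs: difference 1.13 and SD 0.81 (Sample Size Calculation), 1:1 allocation, and "with alpha (α) set to 0.05 and statistical power 0.8" (Analysis of data). I take the test as two-sided: the text says "two-tailed effect sizes will be reported", and only the two-sided version reproduces the stated sizes.

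- d = 1.13/0.81 = 1.395.
- With n per arm, noncentrality λ = d·√(n/2). At n = 12, λ = 1.395 × √6 = 3.417 on 22 df, and power is 90.4%.
- The same t-test calculation gives 10, 11, 12, 15 and 20 per arm for 80, 85, 90, 95 and 99%. All five scenarios match. A one-sided test would give 10 per arm at 90%, which does not match.

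**2. Degrees of freedom if all eight enter.** Position takes 5 − 1 = 4. The other seven take at least 1 each, with socioeconomic and educational level as linear scores. Total 4 + 7 = 11; residual 24 − 2 − 11 = 11. Socioeconomic level as six categories adds 4, giving 15 and leaving 7.

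**3. Where the loss comes from.**

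- Lost df alone (covariates perfectly balanced, R² 0): λ stays at 3.417 on 11 df, and power is 87.4%, a loss of 3 points.
- Chance imbalance: with k normally distributed covariates and 24 players, the expected variance inflation of the group contrast is (24 − 3)/(24 − 3 − k). For k = 11 this is 21/10 = 2.1, and simulation also gave 2.1. This is the larger part of the loss.
- At R² 0 the standard error rises about 42%. The critical t goes from 2.074 to 2.201, so the 95% interval widens by a factor of 1.42 × 2.201/2.074 = 1.51, or about 50%.

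**4. Power with all eight.** λ = 3.417/√[VIF·(1 − R²)], where VIF is the variance inflation, averaged over random imbalance by simulation. R² is my assumption.

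| R² of the covariates | Power, 11 df | Power, 15 df |
|---|---|---|
| 0 | 60% | 41% |
| 0.2 | 69% | – |
| 0.3 | 75% | 52% |
| 0.4 | 80% | – |
| 0.5 | 86% | 66% |
| 0.6 | 92% | – |

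With 11 df, the stated 90% is regained only when the covariates explain between 50 and 60% of the outcome variance.

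**5. Adjusting for the pretest value only.** One follow-up time, pretest-posttest correlation r (assumed). For change from pretest the variance factor is 2(1 − r) on 22 df. For pretest adjustment it is (1 − r²) on 21 df, with expected inflation 21/20 = 1.05 for chance imbalance.

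- r = 0.3: change λ = 3.417/√1.4 = 2.888, power 79%. Pretest-adjusted: 91% with the inflation, 93% without.
- r = 0.6: change λ = 3.417/√0.8 = 3.820, power 95%. Pretest-adjusted: 98%.
- r = 0: pretest-adjusted 89%, against 90.4% for a posttest-only comparison, a cost of about 1.5 points.

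**The case against.** The strongest reply is that the plan never specifies an eight-covariate model. That is correct. Control might be meant partly through design: age is limited to 17–26, only outfield players from one competitive category are eligible, FOCOS is run at the start of the session, and randomisation is itself listed as a bias control. These measures narrow some of the eight but do not fix them, and for several, such as socioeconomic and educational level, nothing but randomisation acts. The sentence remains a promise without a method.

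The statistician is to be masked to group, which limits selective adjustment. It does not prevent it, because the size of the difference between two coded groups is visible under each choice of covariates.

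The power figures are also an analogy. The 90% belongs to one comparison of two means on an unnamed outcome, while the planned IE analysis has four time points. Offensive and defensive IE are averages of proportions with a maximum of 1, so a difference of 1.13 cannot be on their scale. Analysis of data also quotes power of 0.8. These limits stand. The 90% is simply the power basis of the adopted sample size.

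A reader might infer three stronger things that the documents do not support:

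- **That the trial's power will fall to 60–75%.** This needs all eight in the model and an R² of about 0 to 0.3. The documents state neither.
- **That the 11 degrees of freedom do the damage.** Alone they cost 3 points.
- **That the pretest is ignored.** It is one of the four measurements in the repeated-measures analysis. The fair comparator for pretest adjustment is therefore a change-type analysis, and at r = 0.6 the gain is about 3 points.

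**Conclusion.** The point holds as a gap in specification: control of eight variables is promised, no analysis delivers it, and neither the model nor the measurement time is stated. The cost depends on how the gap is filled. With all eight as covariates at 11 df, power for the assumed effect would be about 60% at R² 0, 75% at 0.3, 86% at 0.5 and 92% at 0.6, against 90.4% unadjusted. Treating socioeconomic level as categories lowers it further. These figures rest on the plan's 1.13/0.81, a single two-group comparison, an assumed R² and random imbalance of the covariates. With a subset chosen after the fact, the cost is selective adjustment, which I cannot quantify. It is worth settling before the data are analysed.

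**What to change.** Replace the sentence under Confounding Bias Control, and align Analysis of data, with:

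> The group comparison of each IE over weeks 6, 11 and 16 will use a repeated-measures model with group, time and group-by-time, adjusted for the pretest value of that IE. Age, sporting age, playing position, socioeconomic level, education, mass, BMI and mental fatigue will be described by group at pretest and will not enter the primary model; any further adjustment uses pretest values only, one covariate at a time, as a labelled sensitivity analysis.

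Three details need to go with it:

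- Say what becomes of the Friedman alternative, which cannot carry a covariate or a group term, and of the MANOVA.
- State which pretest mental-fatigue answer is used, since it is asked before both the executive-function tests and FOCOS.
- State whether the same rule applies to the executive-function comparisons.

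**Cost.** No new data are needed, because the pretest is already collected. It is still a change to the main model, not just wording. Chance imbalance in, for example, playing position is handled only in sensitivity analyses. If pretest and later values were uncorrelated, the adjustment would lose about 1.5 points of power against a posttest-only comparison.

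**Gain.** At the single-time level, power is about 91–93% against 79% for change from pretest at r = 0.3, and 98% against 95% at r = 0.6. The route to choosing covariates after seeing results is closed.
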